2.5.1 Subgroups

The following subgroups are defined for AE analysis:

1. Duration of fingolimod treatment up to the end of the long-term follow-up study part I (yearly interval):
 - Year 1 subgroup: patients on fingolimod treatment ≥ 0 year (≥ 1 day)
 - Year 2 subgroup: patients on fingolimod treatment ≥ 1 year (≥ 360 days)
 - Year 3 subgroup: patients on fingolimod treatment ≥ 2 year (≥ 720 days)
 - Year 4 subgroup: patients on fingolimod treatment ≥ 3 year (≥ 1080 days)
 - Year 5 subgroup: patients on fingolimod treatment ≥ 4 year (≥ 1440 days)
 - Year N subgroup: patients on fingolimod treatment $\geq N - 1$ year ($\geq (N - 1) \times 360$ days)
2. Patients from Phase II/III studies: This subgroup includes patients who have enrolled in any of the following studies: D2201, D2301, D2302, and D2309 before entering the long-term follow-up study part I.

3 Patient Disposition

All screen failures in the long-term follow-up study will be listed along with their primary reason for failing screening.

The number and percentage of patients who completed the long-term follow-up study part I, and who discontinued the long-term follow-up study part I, along with the primary reason for discontinuation, will be summarized for the enrolled set. The number and percentage of patients who are expected to have follow-up visits and who returned for 3-month and 6-month follow-up visits will also be summarized.

The patients who discontinued from the long-term follow-up study part I and corresponding reasons will be listed for the enrolled set. Additionally, a similar listing will be provided for the enrolled set of patients from D2312 and D2402 studies who discontinued early from the long-term follow-up study part I.

4 Protocol Deviations

The number and percentage of patients in the enrolled set with each protocol deviation in the long-term follow-up study part I will be displayed by protocol deviation category. Additionally, patients with at least one protocol deviation during the long-term follow-up study part I and patients with at least one protocol deviation causing exclusion from any analysis set (deviation severity codes 0, 5, or 8) will be summarized.

The protocol deviation data will be listed as well.

Additionally, the investigator comments during the long-term follow-up study part I will be listed.

5 Background and demographic characteristics

5.1 Core study

The core study refers to the first fingolimod MS study the patient enrolled in. The number and percentage of patients in each core study prior to transfer into the long-term follow-up study will be provided.

5.2 Demographics

Using data collected from the patient's core study, the following demographic variables will be summarized for the enrolled set and the subgroup of enrolled set patients from phase II/III studies: sex, age (years), age groups [<18 , 18-30, 31-40, 41-55, >55], race, ethnicity, baseline weight, baseline height, and baseline BMI. Baseline height and weight will be derived as the last non-missing assessment prior to first dose of any drug among all studies a patient has participated in. Baseline BMI will be derived based on baseline height and weight. Age will be calculated as the (core study's demographic screening or baseline visit date - patient's birth date +1) / 365.25.

Unless otherwise specified, age is presented in the listings in 3 ways: age 1 is the age at the visit where demographic data is collected (screening or baseline visit of core study); age 2 is the age at first dose of fingolimod among all studies; age 3 is the age at last dose of fingolimod.

5.3 MS disease history characteristics before enrollment in core study

Using data collected from the patient's core study, the following MS disease history characteristics will be summarized for the enrolled set: duration of MS since diagnosis in years, duration of MS since first symptoms in years, number of relapses in the last year prior to enrollment in the core study, number of relapses in the last 2 years prior to enrollment in the core study, time since the onset of the most recent relapse (in months) prior to enrollment in the core study, and duration from MS diagnosis date to last dose date of study drug (in years). The baseline EDSS score and the duration of exposure to fingolimod prior to first dose in the long-term follow-up study part I will also be summarized for the enrolled set. Note that not all parameters are collected across all studies.

The following definitions will be used in calculations involving MS disease history characteristics: one year is defined as 365.25 days and one month is defined as 30 days.

For the MS disease history summary, the variable *Duration of MS since diagnosis* (years) will be derived for each patient as: (first dose date of any study drug among all studies a patient has participated in – the MS diagnosis date + 1)/365.25. *Duration of MS since first symptom* (years) is calculated as (first dose date of any study drug among all studies a patient has participated in – the first MS symptom date + 1) / 365.25. The *time since the onset of the most recent relapse* (months) is computed as (first dose date of any study drug among all studies a patient has participated in – the most recent relapse onset date prior to enrollment in the core study + 1)/30. The duration from MS diagnosis date to last dose date of study drug (in years) is calculated as (last dose date of any study drug among all studies a patient has participated in - the MS diagnosis date + 1)/365.25. Note that the first dose date of any study drug among all studies a patient has participated in may not be fingolimod.

5.4 MRI baseline characteristics

The MRI baseline characteristics will be summarized for number of Gd-enhanced T1 lesions, number of T2 lesions, total volume of T1 hypointense lesions, total volume of T2 lesions, volume of Gd-enhanced T1 lesions and normalized brain volume at both core baseline and fingolimod baseline if applicable. This summary is based on enrolled set.

5.5 MS medication history prior to enrollment in core study

For the MS medication history of disease-modifying drugs (DMDs), treatment-naïve patients are defined as those who never took MS disease-modifying medications prior to enrollment in core study. The number and percentage of treatment-naïve patients and patients who took categories of MS DMDs will be summarized for the enrolled set.

6 Study drug

6.1 Duration of exposure

The duration of exposure to fingolimod study drug will be defined as the number of days from first dose date of fingolimod among all studies to last dose date of the long-term follow-up study part I, excluding the days for which the patient did not take fingolimod (i.e., periods of temporary interruption). The number and percentage of patients being exposed for a minimum of ≥ 1 day, ≥ 90 days, ≥ 180 days, ≥ 360 days, etc. will be presented. Summary statistics of duration of exposure will also be provided. Patient-years of exposure will be reported and is calculated as the (sum of the total number of days on fingolimod study drug for all patients in the treatment group)/365.25. The above summaries will be presented for the fingolimod safety set and the subgroup of fingolimod safety set patients from Phase II/III studies.

Similar summaries will be provided for the duration of exposure to fingolimod study drug during the long-term follow-up study part I, which is defined as the number of days from first dose date of fingolimod in the long-term follow-up study to the last dose date, excluding the days for which the patient did not take fingolimod. Duration of exposure to fingolimod study drug during the long-term follow-up study part I will be presented for the safety set.

The fingolimod dose administration records during the long-term follow-up study part I will be listed for the safety set.

7 Concomitant medication

7.1 Imputation of concomitant medication start date

Missing or partial concomitant medication start dates are imputed following the VDW MAP Module 8 ‘Concomitant Medication Start Date Imputation (#IMPUMED)’ section (displayed below):

Concomitant Medication Start Date Imputation (#IMPUMED)

The following table explains the notation used in the logic matrix. Please note that **missing start dates** will not be imputed.

	Day	Month	Year
Partial CMD Start Date	Not used	MON	YYYY
Treatment Start Date (TRTSTD)	Not used	TRTM	TRTY

The following matrix explains the logic behind the imputation.

	MON MISSING	MON < TRTM	MON = TRTM	MON > TRTM
YYYY MISSING	(C) Uncertain	(C) Uncertain	(C) Uncertain	(C) Uncertain
YYYY < TRTY	(D) Before Treatment Start	(A) Before Treatment Start	(A) Before Treatment Start	(A) Before Treatment Start

YYYY = TRTY	(C) Uncertain	(A) Before Treatment Start	(C) Uncertain	(B) After Treatment Start
YYYY > TRTY	(E) After Treatment Start	(B) After Treatment Start	(B) After Treatment Start	(B) After Treatment Start

The following table is the legend to the logic matrix.

Relationship	
Before Treatment Start	Partial date indicates CMD start date prior to Treatment Start Date
After Treatment Start	Partial date indicates CMD start date after Treatment Start Date
Uncertain	Partial date insufficient to determine relationship of CMD start date to Treatment Start Date
Imputation Calculation	
NC / Blank	No convention
(A)	15MONYYYY
(B)	MAX(01MONYYYY, TRTSTD+1)
(C)	IF CMDTYP1C IN (1, 3) THEN TRTSTD-1 ELSE IF CMDTYP1C IN (., 2) THEN TRTSTD+1
(D)	01JULYYYY
(E)	01JANYYYY

7.3 Concomitant medication analyses

Concomitant medications are defined as medications, other than the study drug, that are reported during the study. All medications recorded on the CFTY720D2399 concomitant medications / significant non-drug therapies CRF will be coded using the current Hybrid DTD_DDE Dictionary. Concomitant medications and significant non-drug therapies, which are recorded in the CFTY720D2399 database and taken at any time from first dose date of fingolimod among all studies to last dose date of fingolimod + 45 days, will be summarized for the safety set by Anatomical Therapeutic Chemical (ATC) class and preferred term. The summary will show the number and percentage of patients receiving at least one drug of a particular ATC class and at least one drug in a particular preferred term (PT). To determine if any particular treatment is needed after discontinuation of fingolimod, concomitant medications and significant non-drug therapies, which are recorded in the CFTY720D2399 database and taken after last dose date of fingolimod, will be summarized in the same way as above for the follow-up set.

Note that concomitant medications which are recorded on the CFTY720D2399 concomitant medications / significant non-drug therapies CRF can include medications that may have been taken during any gap between the completion of the prior study and enrollment into this long-term follow-up study, even if the medication is not ongoing at the time of enrollment.

All concomitant medications recorded during the long-term follow-up study part I will be listed. The concomitant medications taken after study drug discontinuation but up to or after 45 days will be flagged. Records for steroid treatment of MS relapse during the long-term follow-up study part I will be listed for the safety set.

8 Efficacy evaluation

The secondary objective of this study is to evaluate the long-term efficacy of fingolimod 0.5 mg in patients with relapsing forms of MS. [REDACTED]

[REDACTED] Long-term efficacy will be assessed in terms of MS relapse, MRIs, EDSS, MSFC, and health outcomes.

8.1 Analysis of MS Relapses

8.1.1 Relapse date imputations and handling of duplicate relapse records

The start date of a relapse should never be missing. However, missing or partial dates may be expected from some non-phase III trials where data checking may be less vigorous than in phase III trials. To avoid an artificial inflation of the number of relapses by low quality data, missing dates for relapses will only be imputed if the end date of the relapse is after the first dose of the initial study (i.e. if the relapse happened at least partially within the study). If partial or complete end dates are before the first dose date of the initial study, then no imputation will be done. If partial or complete relapse end dates are after the first dose of the initial study, the following algorithm will be applied:

Firstly, drop blanks and impute missing or partially missing start dates

1. Drop complete blanks: If the relapse onset date is invalid (e.g. “No”, “None”) or completely missing and there is no information recorded across all variables, the onset date will be set to missing.
2. Otherwise, if the record is not empty or the onset date is partially missing, check if another record may be available for the same relapse. Concretely:
 - a. If a relapse onset date has a missing day-part (XX-MM-YYYY), where XX represents the missing or invalid part, the onset date will be imputed by the onset date of another treatment-emergent relapse record with a non-missing start date for the same patient within the same month and year, if such a relapse is available (choose the first one if more than one is available).
 - b. If a relapse onset date has a missing day- and month part (XX-XX-YYYY), the onset date will be imputed by the onset date of another treatment-emergent relapse record for the same patient within the same year, if such a relapse is available (choose the first one if more than one is available).
3. Otherwise, if the onset date of a relapse is completely or partially missing, the onset will be imputed with the first possible day within the available non-missing date-part, or the first-dose date, or the relapse end-date minus 90, whatever occurs latest.

Secondly, impute the end date

The imputation of missing or partially missing end dates will be done after the imputation of start dates.

1. If the end date of a relapse is completely missing, it will be imputed as 90 days after the onset date.
2. If the end date of a relapse is partially missing, it will be imputed as the maximum of the relapse start day plus one or the minimum of either 90 days after the onset date, or as the last possible day based on the non-missing parts of the end-date (e.g. XXDEC2007 where XX indicated the missing end day would be imputed as 31-DEC-2007 if the onset date of the relapse was 26-NOV-2007).

Thirdly, handle duplicate relapse records:

After the imputation of start and end-dates is completed, records which refer to the same relapse (30-day rule) will be combined into a new artificial record. This step will help to consolidate core and extension databases where the same relapse may be recorded more than once, and it will help to ensure consistent relapse rules even for studies with a less vigorous date management.

1. For each patient relapses will be sorted by onset date (source or imputed).
2. **Combine relapses for which the distance between onset dates is <30 days:** Starting from the first relapse within each patient, the distance from each relapse to the next will be tested. If the onset date of a relapse is less than 30 days from the onset date of a previous one, an artificial record will be created using the “worst” or “most severe” information from both records (Conservative approach). The following rules apply:

- a. Onset date: use the *minimum* of the candidate dates with the highest degree of completeness. The degree of completeness is defined in descending order: 1. Original date, 2. Only day-part imputed, 3. Day and Month part imputed, 4. Day, Month and Year imputed.

Example: an original date entered by the investigator has the higher degree of completeness compared to a partial/imputed date. An imputed date with just the day-part imputed has the higher degree of completeness compared to a completely imputed date. Rationale: amongst the candidate-dates with the highest reliability/completeness – choose the first/worst.

- b. End date: use the *maximum* of the candidate dates with the highest degree of completeness. The degree of completeness is defined in descending order: 1. Original date, 2. Only day-part imputed, 3. Day and Month part imputed, 4. Day, Month and Year imputed.

Example: an original date entered by the investigator has the higher degree of completeness compared to a partial/imputed date. An imputed date with just the day-part imputed has the higher degree of completeness compared to a completely imputed date. Rationale: amongst the candidate-dates with the highest reliability/completeness – choose the last/worst.

- c. When two records are combined from two consecutive phases (e.g. one from an initial study, the other one from an extension) the combined record will be considered as belonging to the first phase.

Example: A relapse may have started at the end of an extension but ended in an Umbrella study. The same relapse may then be captured in the extension and also in the Umbrella study. When the two records are combined into one, the relapse – according to its start date – will be considered in the extension phase. Programmatically: Ext1n will take the minimum value of the two combined records.

- d. Hospitalization: “yes” is worse than “no”
- e. Severity: “severe” is worse than “moderate” is worse than “mild” is worse than “unknown”
- f. Steroids: “yes” is worse than “no”
- g. Relapse confirmed: “yes” is worse than “no”
- h. Recovery: “none” is worse than “partial” is worse than “complete”
- i. Daily activity: “affected” is worse than “not affected”

Lastly, truncate the duration of all relapses to a maximum of 90 days

1. For each relapse record, check whether the duration from onset to end date is less or equal to 90 days, if this is not the case do the following:
 - a. Determine the degree of completeness of the start and end-date. The degree of completeness is defined in descending order: 1. Original date, 2. Only day-part imputed, 3. Day and Month part imputed, 4. Day, Month and Year imputed.

Example: an original date entered by the investigator has the higher degree of completeness compared to a partial/imputed date. An imputed date with just the day-part imputed has the higher degree of completeness compared to a completely imputed date.
 - b. Keep the date with the higher degree of completeness fixed and update the other date, so that the duration the relapse is maximized to 90 days

Rationale: If one of the dates has to be replaced to keep truncate the duration of the relapse to 90 days, keep the date with the higher degree of completeness/reliability fixed (either the end- or the start date) and replace the other one.
 - c. If the onset- and end-date have the same degree of completeness, keep the start date fixed and impute the end-date such that the duration of the relapse is maximized to 90 days.
2. If a relapse is recorded as ongoing at the final exam, impute an end date such that the duration is maximized to 90 days.

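### In both SAPs, the relapse-date rules let a partial onset leave its recorded month or year, and let a year-only relapse be merged into a relapse it cannot belong to

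*SAP*

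**What the plan says.** SAP Part I section 8.1.1, repeated in SAP Part 2 section 8.1.1, handles relapse dates in this order.

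- **Gate.** The stated aim is "To avoid an artificial inflation of the number of relapses by low quality data", so "missing dates for relapses will only be imputed if the end date of the relapse is after the first dose of the initial study".
- **Step 2a (day missing).** The record takes the onset of "another treatment-emergent relapse record with a non-missing start date for the same patient within the same month and year".
- **Step 2b (day and month missing).** Here "the onset date will be imputed by the onset date of another treatment-emergent relapse record for the same patient within the same year". Unlike 2a, this does not require the other record's start date to be non-missing.
- **Step 3 (no match found).** Three candidates are compared. One is the earliest day that the recorded part allows; the others, and the choice among them, read "or the first-dose date, or the relapse end-date minus 90, whatever occurs latest".
- **Merging.** "If the onset date of a relapse is less than 30 days from the onset date of a previous one", the two records are combined into one.
- **Truncation to 90 days.** "Keep the date with the higher degree of completeness fixed and update the other date". If both dates are equally complete, the start stays and the end is cut.

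The resulting onsets feed the annualized relapse rate (ARR) by interval, the yearly relapse summaries and the Kaplan-Meier time to first relapse (sections 8.1.2 to 8.1.4), all measured from the first fingolimod dose.

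**The concern.** Step 3 takes the latest of three dates and has no upper limit at the end of the recorded month or year. A known month can therefore be overwritten because only the day is missing. If the recorded part lies wholly before first dose, the first-dose term turns a pre-treatment onset into an on-treatment one. Step 2b is meant to find another record of the same relapse, but it accepts any treatment-emergent relapse in that year.

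Onset decides whether and where a relapse counts. Time to first relapse is defined by onset, and the SAP's own example for combined records assigns the relapse to a phase by its start date. A misplaced onset can add a pre-treatment or comparator relapse to the fingolimod count, shift an event to a later interval, or, through merging, remove an event.

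The SAP does not treat other partial dates this way. The general rule (section 2.4) keeps the recorded month and year. The adverse-event and concomitant-medication rules (Part I sections 9.1.1 and 7.1) place a recorded month earlier than the treatment-start month on the 15th of that month and class it as before treatment.

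**Working it through.** The rules come from section 8.1.1. The records below are constructed to test them; they are not trial data.

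**The plan's own example.** Imputed end = max(onset + 1, min(onset + 90, last possible day)). For onset 26-NOV-2007 and an end in December 2007: max(27-NOV-2007, min(24-FEB-2008, 31-DEC-2007)) = 31-DEC-2007, as the SAP states.

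**Step 3.** Imputed onset = max(first possible day, first-dose date, end − 90).

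1. *Pre-dose month.* Onset XX-JAN-2010, first dose (fingolimod, initial study) 15-MAR-2010, end 20-MAR-2010. The gate is passed because the end is after first dose. max(01-JAN-2010, 15-MAR-2010, 20-DEC-2009) = 15-MAR-2010, which is Day 1. The true onset is 31-JAN-2010 at the latest, 43 days before first dose. No overlong relapse is needed: onset to end is between 48 days (from 31 January) and 78 days (from 1 January).
2. *Long record.* Onset XX-MAR-2010, end 30-SEP-2010, first dose 15-JAN-2008. max(01-MAR-2010, 15-JAN-2008, 02-JUL-2010) = 02-JUL-2010, which is 93 days after 31 March and 123 days after 1 March. A complete onset of 10-MAR-2010 with the same end stays in March, and its end is cut instead.
3. *Comparator patient.* Onset XX-MAR-2008, first fingolimod dose 01-JUN-2008, end 15-SEP-2008. End − 90 = 17-JUN-2008, which is later than both 01-MAR-2008 and 01-JUN-2008. The imputed onset is 17-JUN-2008, on fingolimod, whether the first-dose date means that of the initial study (if before March 2008) or that of fingolimod.
4. *Interval boundary.* First fingolimod dose 15-JAN-2010, onset XX-DEC-2010, end 10-MAY-2011. End − 90 = 09-FEB-2011, Day 391. The last day of the recorded month is Day 351, so the event moves from Month 0–12 to Month 12–24.

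*When the end − 90 term matters.* For an onset after first dose, it leaves the recorded part only if the end is more than 90 days after that part's last day: after 29-JUN-2010 for March 2010, or after 31-MAR-2011 for a year-only 2010 onset.

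**Step 2b and merging.** One relapse runs from 10-FEB-2010 to 01-MAR-2010. A second is recorded only as 2010, ending 20-NOV-2010.

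- Step 2b gives the second record onset 10-FEB-2010. The onsets are 0 days apart, so the under-30-day rule must merge them.
- The combined record runs to 20-NOV-2010, 284 days counting both ends, and is cut to 90.
- Under the same 90-day limit the second relapse could not begin before 20-NOV-2010 − 90 = 22-AUG-2010, which is 193 days after 10-FEB-2010. Protocol section 6.4.1 treats onsets at least 30 days apart as separate relapses.
- Over two years of follow-up, this patient's ARR falls from 2/730.5 × 365.25 = 1.0 to 1/730.5 × 365.25 = 0.5.

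Step 2a is nearly harmless: two onsets in one month are at most 30 days apart, against up to 364 days within one year.

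**Truncation.** Step 3 already forces onset ≥ end − 90, so truncation has little left to move under the current rules. If step 3 alone were repaired, record 2 would have onset 31-MAR-2010 and a complete end 183 days later. Truncation would then hold the end, move the onset back to July and undo the repair.

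**The case against.** Four points can fairly be made for the plan.

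*Counting relapses that overlap first dose is deliberate.* The gate admits a relapse that fell at least partly within the study. That stands as a reason to keep such records. It does not say that a known pre-dose onset becomes Day 1, and a complete January 2010 onset would not be moved. If overlap is meant to count, the SAP should say so for complete and partial dates alike.

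*Records 2 to 4 exceed the 90-day limit, so one date has to give way, and the SAP ranks dates by completeness.* It is true that the end − 90 shift needs a long record. But the recorded month is not in doubt, and one missing day reverses which date yields. Record 1 does not depend on the limit at all.

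*Borrowing and merging serve a purpose.* They combine core and extension records and also clean studies with weaker date management. This stands: genuine duplicates can occur inside one database, so restricting borrowing to records from different databases would miss them, and would still merge distinct relapses across databases. The useful test is the record's own end date.

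*The consequence is limited.* Start dates should never be missing, and gaps are expected only from some non-phase III trials. Record 2 changes no count. Section 8.1.2 already warns of another distortion, uncountable and off-study time kept in the ARR denominator. This bears on size; it does not make the rule correct.

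**Conclusion.** The point holds. As written, step 3 can place an onset outside its recorded month or year, including from before treatment onto Day 1 and from comparator onto fingolimod. Step 2b can force a merge that the record's own end date rules out. The first-dose date in step 3 is also undefined: the gate refers to the initial study, while the analyses run from first fingolimod dose. On the second reading, any comparator-period partial onset reaching step 3 would move to fingolimod Day 1 or later, even if the relapse had already ended.

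Per affected record, the effect is one relapse added, one lost, or one moved by roughly three to four months in record 2. The total is unknown because the documents do not give the number of partial onsets. The direction is mixed: pre-dose and comparator shifts raise the fingolimod count, forced merges lower it, and other shifts lengthen relapse-free time. The reasoning assumes that relapses are counted by onset, as the Kaplan-Meier definition and the phase-assignment example indicate. Relapse is a secondary, descriptive endpoint, and the primary safety analyses are untouched.

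Two stronger readings are tempting. A reader might infer that the 90-day truncation causes the same shift on its own. Under the current rules it does not, apart from corner cases such as two partial records merging or a one-day counting difference. A reader might also turn an assumed relapse rate into a share of year-only relapses lost. The documents give no basis for that, and some year-only records will be true duplicates.

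**What to change.** Amend section 8.1.1 in both SAPs.

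- **(a) Step 3.** Keep the imputed onset within the recorded month or year. If that part ends before first dose, treat the onset as pre-treatment. State whether the first-dose date is that of the initial study or of fingolimod. Record 1 becomes pre-treatment, record 2 falls no later than 31-MAR-2010, record 3 stays in the comparator period, and record 4 returns to Month 0–12.
- **(b) Truncation, as a consequence of (a).** Keep the onset within its recorded month or year and shorten the end date for whatever remains above 90 days.
- **(c) Step 2b.** Borrow another relapse's onset only if that onset is complete and compatible with the record's own end date under the 90-day limit. Otherwise keep a separate event. The step 2b example then gives two relapses, the second imputed to 22-AUG-2010 if first dose was earlier. The text should also say what applies when the record's own end date is missing.

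The cost is a few lines of SAP text and derivation code, with no new data. Reporting how many relapse records had a partial onset, and how many were borrowed and merged, would show the size of the effect.
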